## STUDY PROTOCOL

This study was a randomized controlled trial of healthy participants. After providing written informed consent, participants were screened for eligibility criteria. Eligible participants then underwent Quantitative Sensory Testing procedures that included Heat Pain Threshold (HPT), Temporal Summation (TS), Pressure Pain Threshold (PPT), and Conditioned Pain Modulation (CPM).

During HPT, participants were provided a thermode attached to a TCS-II (QST.Lab, Strasbourg, France). The thermode increased from a baseline of 32 degrees Celsius at 1 degree C/second to a maximum of 50 degrees Celsius. Participants were instructed to indicate when the sensation first changed from warmth to pain (pain threshold) by pressing a button. Once the button was pressed, the temperature stopped increasing and quickly returned to a baseline temperature of 32 degrees Celsius. Two trials were completed at the dominant quadriceps and ipsilateral upper trapezius.

During TS, participants placed the thermode on the palmar surface of the hand. Participants rated the pain intensity during a train of 10 heat pulses that were delivered to the skin with temperatures peaking at 49°C at a rate to maintain the desired inter-stimulus interval.

For PPT, a computerized pressure algometer (AlgoMed, Ramat Yishai, Israel) with a 1 cm diameter rubber tip was applied at a constant rate. Participants were instructed to press a response button connected to the algometer when the sensation first changed from pressure to pain (pain threshold). Two trials were performed at the dominant quadriceps and ipsilateral upper trapezius.

For CPM, PPT was applied to the web space of the non-dominant foot. Participants then immersed the dominant hand into water cooled by a refrigeration unit (ARCTIC Series Refrigerated Bath Circulator, ThermoFisher Scientific, Massachusetts, USA) that circulated water continuously to maintain a constant temperature of 12° Celsius for 60 seconds. PPT measurement was then repeated.

After Quantitative Sensory Testing, participants completed a 1-repetition maximum test for a leg extension exercise with the dominant lower extremity.

Participants were then randomly assigned to either the high intensity exercise, low intensity exercise, or quiet rest intervention. For participants assigned to the exercise interventions, individuals completed a single leg knee extension exercise for 3 sets, 10 repetitions on the dominant leg. A weight corresponding to either 30% or 75% of the participants 1-repetition maximum was added for the low intensity or high intensity group, respectively. For individuals assigned to the quiet rest intervention, participants sat quietly for two minutes three sets. Between each set or exercise or quiet rest, PPT was measured on the dominant quadriceps and upper trapezius.

After exercise, CPM was repeated.

## STATISTICAL ANALYSIS

To examine the immediate changes in PPT by group, a mixed model ANOVA was conducted. Simple effects decomposition with Bonferroni correction were completed. Our a priori alpha level is <0.05.

A Pearson correlation examined for the association of HPT, TS, baseline PPT with Exercise-Induced Hypoalgesia.

To examine if CPM efficiency changes by group, a mixed model ANOVA was conducted.

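### The follow-up to the three-arm PPT analysis does not adjust for pre-randomisation PPT and names no between-arm contrast; baseline-adjusted contrasts would be sharper and need no new data

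*Combined protocol and SAP*

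**What the plan says.** The STUDY PROTOCOL section describes three randomised arms: "Participants were then randomly assigned to either the high intensity exercise, low intensity exercise, or quiet rest intervention". Before assignment, PPT is taken at two sites: "Two trials were performed at the dominant quadriceps and ipsilateral upper trapezius". After assignment it is taken repeatedly at the same sites: "Between each set or exercise or quiet rest, PPT was measured on the dominant quadriceps and upper trapezius". The exercise arms perform three sets, so there are at least two post-randomisation readings per site. A reading after the third set is not explicit.

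The STATISTICAL ANALYSIS section gives the PPT inference in three sentences: "To examine the immediate changes in PPT by group, a mixed model ANOVA was conducted"; "Simple effects decomposition with Bonferroni correction were completed"; and "Our a priori alpha level is <0.05". It does not list the factors of the model, say whether the simple effects are of arm at each time or of time within arm, name a pairwise arm comparison, define the Bonferroni family, or mention baseline PPT as a covariate.

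**The concern.** The design asks whether each exercise intensity changes PPT relative to rest, and whether the two intensities differ. With three arms, a significant group-by-time term says only that the arms do not all follow the same course. The follow-up has to say which arms differ and by how much, and its meaning depends on its direction.

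- **Arm at each time.** This is a randomised comparison and valid. On raw PPT it leaves the pre-randomisation value unused. On change scores it uses that value, but not in the most efficient way.
- **Time within arm.** This describes each arm's own course and does not test a difference between arms.

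At stake in the first case is power, and in the second the basis for any claim that arms differ. The main point is the first: a better contrast can be had from data the trial already collects.

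**Working it through.** **Inputs from the documents:** three arms; two sites; PPT before randomisation at both; repeated PPT afterwards; alpha 0.05. The documents give no sample size, power, SD, effect or correlation, so there is no planned figure to reproduce.

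**Assumptions for illustration:** 20 per arm; high intensity 0.6 SD above rest at every post reading; SD 1; the same correlation ρ between any two readings; two-sided alpha 0.05/3 = 0.0167.

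**Step 1: relative variance of a between-arm contrast at one post reading** (raw PPT = 1).
- Change score: 2(1−ρ), which is 1.20, 0.60, 0.40 at ρ = 0.4, 0.7, 0.8.
- Baseline-adjusted: 1−ρ², which is 0.84, 0.51, 0.36.

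Apart from one degree of freedom, adjustment is never worse than either. It cannot exceed 1, and 2(1−ρ) − (1−ρ²) = (1−ρ)², which is never negative. At ρ = 0 it equals raw PPT. Below ρ = 0.5 the change score is worse than raw PPT.

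**Step 2: the same for the mean of two post readings.** The mean has variance (1+ρ)/2 and covariance ρ with baseline.
- Change in the mean: 1.5(1−ρ), which is 0.90, 0.45, 0.30.
- Baseline-adjusted mean: (1+ρ)/2 − ρ², which is 0.54, 0.36, 0.26.

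**Step 3: power.** The signal-to-noise ratio is 0.6/√(2v/20), with v the relative variance. At ρ = 0.7 it is 1.90 for raw PPT, 2.66 for the adjusted single reading and 3.16 for the adjusted mean, against a critical value of about 2.47. Simulated power, which varies by one or two points between runs and with the choice of error term:

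| Contrast, high vs rest | ρ 0.4 | ρ 0.7 | ρ 0.8 |
|---|---|---|---|
| One reading, raw PPT | 29% | 29% | 29% |
| One reading, change score | 24% | 48% | 70% |
| One reading, baseline-adjusted | 34% | 56% | 75% |
| Mean of two readings, change score | 33% | 64% | 83% |
| Mean of two readings, baseline-adjusted | 54% | 74% | 88% |

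At one reading, adjustment gains 5, 27 and 46 points over raw PPT and 10, 8 and 5 over change scores. Using the mean of both readings instead of one gains a further 20, 18 and 13 points, which depends on the effect being constant across readings.

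**Step 4: sensitivity to sample size.** At ρ = 0.7 and one reading, going from 12 to 40 per arm moves power from 16% to 60% (raw), 28% to 85% (change) and 33% to 90% (adjusted). The ordering does not change.

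**Step 5: the Bonferroni family.** With three or four time points (baseline included) and one or two sites, pairwise tests of arm at each time number 3 × 3 × 1 = 9 up to 3 × 4 × 2 = 24. Pairwise tests of time within arm number 3 × 3 × 1 = 9 up to 6 × 3 × 2 = 36. The per-test level could thus lie anywhere from 0.05/9 = 0.0056 to 0.05/36 = 0.0014.

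**The case against.** The strongest reply is that nothing planned is shown to be invalid. The group-by-time test is a randomised comparison, arm at each time is a valid follow-up, and preferring adjustment over raw or change scores is a matter of efficiency. That stands, and it sets the size of the point. The gain over change scores is 5 to 10 points in the illustration, and the gain over raw PPT disappears as ρ approaches zero. A high ρ should not be presumed, because the CPM cold-water immersion and the one-repetition maximum test fall between baseline PPT and the intervention.

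A second reply is that an adjusted contrast at the last reading alone would waste the earlier readings. That also stands. Under the same assumptions, an unadjusted change in the mean of two readings (64% and 83% at ρ = 0.7 and 0.8) beats an adjusted last-reading contrast (56% and 75%). The recommendation below therefore uses all post readings by default.

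A reader might infer that the trial will declare arms different because one shows a significant within-arm change and another does not. The documents do not support this. They do not give the direction of the simple effects, and they do not say that p-values will be compared across arms. The harm would also depend on an assumed shared drift. With 0.3 SD of drift, a Bonferroni divisor of three and low intensity truly equal to rest, the pattern of low significant and rest not, together with a significant group-by-time test, arises in 3/12/20% of trials at ρ = 0.4/0.7/0.8. With drift of 0 to 0.1 SD it is about 1 to 3%. A shared drift of that size has no basis in the documents.

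**Conclusion.** The concern holds as a worthwhile improvement. The planned follow-up does not adjust for a baseline that is available at both sites, and it does not identify the contrasts that would answer the trial's question. Where baseline and later PPT are correlated, the baseline-adjusted contrast is more efficient than arm-at-each-time comparisons on raw PPT, and it is more efficient than change scores at any correlation below one. How much more cannot be known from the documents; the figures above rest on assumed sample size, effect and correlation.

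The analysis is not shown to be biased, nor the omnibus test to be wrong. That time-within-arm effects should not support claims of arm differences is a caution about an open wording. The unstated direction and family would, taken alone, be missing detail.

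**What to change.** Keep the group-by-time test as the overall test. As its follow-up, estimate three between-arm contrasts (high vs rest, low vs rest, high vs low) at each site, adjusted for that site's pre-randomisation PPT, with confidence intervals.

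- **Readings.** By default use every post-randomisation reading taken in all arms, for example ANCOVA on their mean or a repeated-measures model with baseline as covariate. Use only the last common reading if the aim is the effect after all the exercise has been completed. In that case name the reading, say whether it follows the second or third set, and state that the choice costs about 13 to 20 points of power in the illustration if the effect is constant across readings.
- **Family.** Apply Bonferroni over three contrasts (0.0167) if each site supports a separate claim, or over six (0.05/6 = 0.0083) if one claim spans both sites, and say which.
- **Within-arm changes.** Report them as descriptive only.
- **Labelling.** The section is written in the past tense, so label these contrasts post hoc unless an earlier plan names them.

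The cost is one degree of freedom, and within-arm p-values no longer support claims of arm differences. Choosing six tests over three costs about 9 to 10 points of power in the illustration at one reading. No new data are needed.

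### Holm's step-down over the same family would control the same error as the planned Bonferroni correction and never reject less; an optional gain, provided the family is stated

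*Combined protocol and SAP*

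**What the plan says.** Under STUDY PROTOCOL there are three arms: "Participants were then randomly assigned to either the high intensity exercise, low intensity exercise, or quiet rest intervention". PPT is measured repeatedly and at two sites: "Between each set or exercise or quiet rest, PPT was measured on the dominant quadriceps and upper trapezius".

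Under STATISTICAL ANALYSIS the main PPT analysis is given as "To examine the immediate changes in PPT by group, a mixed model ANOVA was conducted", followed by "Simple effects decomposition with Bonferroni correction were completed" and "Our a priori alpha level is <0.05".

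The text does not say whether the simple effects compare arms within a time point or time points within an arm. It does not give the number of comparisons in the Bonferroni family, or say whether the two sites share a family. It states no sample size, SD, effect size or power.

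**The concern.** Bonferroni tests each of k comparisons at 0.05/k, whatever the other comparisons show. Holm orders the p-values and tests them at 0.05/k, 0.05/(k-1), and so on up to 0.05, stopping at the first failure. Both control familywise error at 0.05 under any dependence between the tests. Every Holm threshold is at least as large as Bonferroni's, so Holm can only add rejections.

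At stake are the comparisons that do not have the smallest p-value. If the family is the three arm pairs, high versus low is the contrast that uses both exercise intensities. Where it is smaller than high versus rest, it is tested under Bonferroni at a stricter threshold than familywise control requires.

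**Working it through.** **Inputs from the documents.** Alpha 0.05 (STATISTICAL ANALYSIS; two-sided assumed, since sidedness is not stated) and three arms (STUDY PROTOCOL). There is no planned power or sample size to reproduce.

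**Assumptions.** The family is the three arm pairs at one time point and one site. Allocation is equal with 20 per arm. The outcome is normal with SD 1 in every arm, and two-sided t tests use the pooled variance on 3 × 19 = 57 degrees of freedom.

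**Thresholds for k = 3.**
- Bonferroni: 0.05/3 = 0.0167 for all three.
- Holm: 0.0167, then 0.05/2 = 0.025, then 0.05.
- Shaffer: 0.0167, then 0.05 and 0.05.

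**Error control.** If the three tests were independent, Bonferroni would give 1 − (1 − 0.0167)³ = 0.049. In simulation with all arms equal, Bonferroni and Holm both give 4.2% to 4.5% over 10 to 50 per arm. They agree because their first step is the same test. With only the high arm shifted, by 0.8 SD at 20 per arm, low versus rest is falsely rejected in 1.7% (Bonferroni), 3.0% (Holm) and 4.8% (Shaffer) of trials.

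**Power for high versus low, 20 per arm.** At least 30,000 simulated trials per row; a repeat with 200,000 agreed within about a point.

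| Means rest, low, high (SD) | Bonferroni | Holm | Shaffer | Any rejection, all three methods |
|---|---|---|---|---|
| 0, 0.25, 0.5 | 5.3% | 6.2% | 8.1% | 24.0% |
| 0, 0, 0.8 | 52.9% | 56.2% | 60.8% | 69.3% |
| 0, 0.5, 1.0 | 19.6% | 25.1% | 32.3% | 77.9% |
| 0, 0.6, 1.2 | 29% | 38% | 46% | 91% |
| 0, 0.8, 1.6 | 52.6% | 65.8% | 69.7% | 99.5% |

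Holm's gain is 6.2 − 5.3 = 0.9 points in the first row, 38 − 29 = 9 in the fourth and 65.8 − 52.6 = 13.2 in the last. Over 10 to 50 per arm, and high-arm shifts of 0.8 to 1.6 SD with the low arm at zero or half that shift, Holm's gain for a true high-versus-low or low-versus-rest difference runs from 1.2 to 13.7 points.

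**What the correction itself costs.** A contrast with 80% power at 0.05 has Φ(1.960 + 0.842 − 2.394) = Φ(0.408) = 0.658, or 66%, at 0.0167. This compares uncorrected tests with Bonferroni. It is not the gain from Holm, which recovers only part of the gap, and only after another rejection.

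**If the family is not three arm pairs.**
- *One time effect per arm.* The three null hypotheses are then logically unrelated. With one true effect, Shaffer's second step tests two true nulls at 0.05 each, and familywise error can reach 1 − 0.95² = 9.75%. Holm keeps it at 0.05.
- *A family spanning times and sites.* Splitting it into separate 0.05 families would loosen control. Two sites by two or three time points make 4 to 6 families, and 1 − 0.95⁴ = 18.5% to 1 − 0.95⁶ = 26.5% if they were independent (less with correlation). Holm over the whole family avoids this.

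**The case against.** Bonferroni is a valid method, named in the plan, and it comes with simultaneous confidence intervals that match its decisions. Holm has no equally simple intervals: reporting Bonferroni-width intervals beside Holm decisions can show a significant contrast whose interval includes zero. The family is also undefined. The stated aim fits time effects within each arm just as well, and that family would contain no high-versus-low contrast. The section is written in the past tense, so a more liberal test adopted now could be post hoc.

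All of this stands, and it makes the point optional. It does not remove it, because Holm's advantage over Bonferroni holds for any family, whatever its direction or size.

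Two stronger readings are tempting:
- A reader might infer that real high-versus-low or low-versus-rest differences are being missed. The documents give no sample size, SD, effect or result to show this. In the small-effect row all three methods have power below 10%, and even Shaffer's 46% in the fourth row leaves a non-significant result more likely than not.
- A reader might infer that three arms license Shaffer's thresholds at each time point. The documents define neither the direction nor the extent of the family, so this may fail to hold the planned error rate.

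**Conclusion.** The point holds as a minor, optional efficiency improvement. For whatever family is intended, Holm controls the same familywise error as Bonferroni without further assumptions and never rejects less. The chance of any rejection does not change; only contrasts tested after a first rejection can gain.

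For three arm pairs and an assumed 20 per arm, Holm adds about 1 to 9 points of high-versus-low power from (0, 0.25, 0.5) to (0, 0.6, 1.2) SD, with more possible at larger effects. These figures rest on the assumed family, arm size, effects and normal outcome; none comes from the documents. Gains for larger families were not calculated. Nothing here makes the planned Bonferroni analysis wrong.

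**What to change.** In STATISTICAL ANALYSIS, replace the reference to a Bonferroni correction with: *Holm step-down correction over the same family of simple-effect comparisons*. State that family in the same place: arms within time or times within arm, which time points, and whether the quadriceps and upper trapezius are in one family or separate ones. Do not make the family smaller than the one Bonferroni was meant to cover.

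Shaffer's thresholds (0.05/3, then 0.05 and 0.05) may be used only if the family is exactly the three pairwise arm comparisons.

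The cost is one or two sentences and no new data; Holm needs only the unadjusted p-values. The downside is the loss of simple matching simultaneous intervals. If Bonferroni-width intervals are kept, say that they may disagree with the Holm decisions. If results have already been seen, report Holm beside the planned Bonferroni result and label it as a change to the plan.

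### Correlating baseline PPT with Exercise-Induced Hypoalgesia is biased away from zero if hypoalgesia is the change from that same baseline

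*Combined protocol and SAP*

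**What the plan says.** The STATISTICAL ANALYSIS section gives the association analysis one sentence: "A Pearson correlation examined for the association of HPT, TS, baseline PPT with Exercise-Induced Hypoalgesia". It states no formula, site, time point or sign for EIH, and does not say which arms are included. It gives no null value for the correlation. The significance level, "Our a priori alpha level is <0.05", appears in the ANOVA paragraph.

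The STUDY PROTOCOL section describes baseline PPT as part of the sensory testing before randomization: "Two trials were performed at the dominant quadriceps and ipsilateral upper trapezius". How the two trials are combined is not stated. During the intervention, "Between each set or exercise or quiet rest, PPT was measured on the dominant quadriceps and upper trapezius". These are the same two sites, and no other pre-intervention PPT is described there. The only PPT outcome named is the one in "To examine the immediate changes in PPT by group, a mixed model ANOVA was conducted".

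**The concern.** If EIH is later PPT minus baseline PPT at the same site, the baseline reading is both the predictor and the subtracted term. A participant whose baseline happens to read low gets a low predictor value and an inflated gain. This produces a negative correlation with no biological link behind it, which is regression to the mean.

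A significant negative r could then be reported as showing that people with lower pain thresholds gain more hypoalgesia from exercise, when part or all of it is artefact. Quiet rest has the same repeated PPT readings, so the same correlation would be expected there without any exercise.

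**Working it through.** The plan states no expected r, sample size, PPT variance or reliability, so it has no figure to reproduce. The check asks what the test does when there is no true association.

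**Inputs from the documents.** Pearson correlation; alpha 0.05; two baseline trials per site; later PPT at the same sites; three arms.

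**Assumptions.** Two-sided test of r = 0; change coded as later minus baseline (reverse coding flips the sign of the bias, not its size); reliability R, true-change variance and n as shown below. Baseline and later readings appear to come from one session, so R means within-session reliability.

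**Model.** Baseline B = T + e1 and later reading P = T + D + e2. True change D is independent of true baseline T, and the errors are independent. Scale so that Var(B) = 1, Var(T) = R and Var(e1) = Var(e2) = 1 − R. Then

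- P − B = D + e2 − e1
- Cov(B, P − B) = −(1 − R)
- Var(P − B) = Var(D) + 2(1 − R)
- expected r = −(1 − R) / √[Var(D) + 2(1 − R)]

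For R = 0.8 and Var(D) = 0.1: −0.2 / √(0.1 + 0.4) = −0.28.

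Expected r with no true association:

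| Var(D) | R = 0.7 | 0.8 | 0.9 | 0.95 |
|---|---|---|---|---|
| 0 | −0.39 | −0.32 | −0.22 | −0.16 |
| 0.1 | −0.36 | −0.28 | −0.18 | −0.11 |
| 0.2 | −0.34 | −0.26 | −0.16 | −0.09 |

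False-positive rate of the nominal 5% test (20,000 simulated trials per cell):

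| Baseline used | n | Var(D) | R = 0.7 | 0.8 | 0.9 | 0.95 |
|---|---|---|---|---|---|---|
| Single reading | 40 | 0 | 71% | 52% | 29% | 16% |
| Single reading | 40 | 0.1 | 63% | 43% | 20% | 10% |
| Single reading | 40 | 0.2 | 58% | 37% | 16% | 8% |
| Single reading | 20 | 0.1 | 36% | 23% | 12% | 8% |
| Single reading | 60 | 0.1 | 82% | 60% | 29% | 14% |
| Mean of two trials | 40 | 0 | 33% | 22% | 13% | 9% |
| Mean of two trials | 40 | 0.1 | 28% | 18% | 10% | 7% |

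**Averaged trials.** In those rows R is the reliability of one trial, and there is one later reading. The error variance of the mean is (1 − R)/2, and the variance of the mean is R + (1 − R)/2 = (1 + R)/2. Expected r is then −[(1 − R)/2] / √{[(1 + R)/2] × [Var(D) + 1.5(1 − R)]}. For R = 0.8 and Var(D) = 0.1: −0.1 / √(0.9 × 0.4) = −0.17. Averaging shrinks the bias but does not remove it.

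**Percent change.** With lognormal PPT, a coefficient of variation of 0.3, Var(D) = 0.1 on the log scale and n = 40, the rates are 61%, 40%, 19% and 10%. Expressing EIH as a percentage does not solve the problem.

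**Where it does not arise.** HPT and TS are separate measurements. Pairing baseline at one site with change at the other also avoids the coupling, provided the errors at the two sites are independent.

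**The case against.** - **EIH is undefined, so the coupling is one reading of the plan.** This stands as a limit: the documents do not confirm the definition, and a cross-site pairing would escape. But no other baseline at those sites is described, and a missing definition also needs correcting.
- **Neither the r = 0 null nor the negative sign is written down.** True. The null is the default for a Pearson test, and the sign follows the coding of the change. Neither removes the bias.
- **The largest rates are the least applicable.** Largely fair. Two trials were taken, so the averaged rows may be closer to practice; if the later value is averaged too, the rates are about 37%, 22%, 11% and 7% (Var(D) = 0.1, n = 40). Var(D) = 0 means that no one's true response differs, so no predictor could be related to it. With Var(D) = 0.5 and an averaged baseline the rates fall to 18%, 11%, 7% and 5%. With high reliability and a widely varying response, the bias is negligible. The documents give no figures that would place this trial there.
- **Splitting the trials needs independent errors.** This stands. If the two trials' errors correlate at 0.5 (assumed), split trials reject in 20% of cases at R = 0.7, Var(D) = 0.1 and n = 40. The averaged baseline rejects in 47% under the same conditions, so splitting is still the better choice.
- **The reach is small.** Agreed: it concerns one of three predictors in one association analysis.

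**Conclusion.** The concern holds on the condition that EIH is the same-site change from the sensory-testing baseline. For any reliability below 1, the expected correlation under no true association is not zero, and the planned test has no adjustment for this. The direction is certain once the coding of the change is known. The size is not: over the assumed ranges the false-positive rate runs from about 5% to 82%, and at n = 40, Var(D) = 0.1 and an averaged baseline it is 7% to 28%. The randomized PPT comparison, the CPM analysis and the HPT and TS correlations are unaffected. This should be fixed, but it does not threaten the trial's main comparison.

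**What to change.** State the EIH formula, site and time point. The time point matters because the protocol places the PPT readings between sets and does not clearly describe one after the last set. Keep HPT and TS in the Pearson analysis, take baseline PPT out, and use one of the following.

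- **(a) Interaction with quiet rest.** Regress the chosen later PPT on group, baseline PPT and baseline PPT × (exercise versus quiet rest), and test the interaction with robust standard errors, because residual variance may differ by arm. Regression to the mean affects both slopes, so the quiet-rest slope absorbs it. With 40 exercise and 20 rest participants (assumed), the HC3 test rejects in 4.1% to 5.0% of null trials.
- **(b) Split trials.** Use one baseline trial as predictor and the other as the reference in the change score. With independent trial errors the rejection rate is 4.8% to 5.3% at n = 40. This requires that trial-level values were kept.

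Do not correlate the change with the mean of the pre and post values. That is biased upward when true response varies: at Var(D) = 0.1, r is about +0.06 to +0.09.

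The cost is one regression or one recomputed score, with no new data. The price is precision. For an assumed slope of true change on true baseline of −0.3, with Var(D) = 0.1 as the remaining variance of true change, power at R = 0.7, 0.8, 0.9 and 0.95 is about 16%, 26%, 47% and 73% for (a), and 32%, 52%, 83% and 96% for (b) at n = 40. Option (a) also answers a between-arm moderation question rather than a within-exercise one. The plan is written in the past tense, so if the data have already been analysed the result should be labelled a re-analysis.

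### The predictor analysis leaves the number of correlations open (3, 6, 10 or more, depending on unstated site, time-point and group choices) and plans no multiplicity correction for them

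*Combined protocol and SAP*

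**What the plan says.** The predictor analysis is a single sentence in the Statistical Analysis section: "A Pearson correlation examined for the association of HPT, TS, baseline PPT with Exercise-Induced Hypoalgesia". It names three predictors: heat pain threshold (HPT), temporal summation (TS) and baseline pressure pain threshold (PPT). It names one outcome, which is not defined by site, time point or formula.

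The Study Protocol section shows that most of these quantities exist at more than one site:
- HPT: "Two trials were completed at the dominant quadriceps and ipsilateral upper trapezius".
- Baseline PPT: "Two trials were performed at the dominant quadriceps and ipsilateral upper trapezius".
- TS: the palm only.
- PPT response between sets: "PPT was measured on the dominant quadriceps and upper trapezius".

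On error control, the paragraph on the PPT ANOVA reads "Simple effects decomposition with Bonferroni correction were completed. Our a priori alpha level is <0.05". The correlation paragraph that follows gives no alpha, no correction, no primary pair and no exploratory label.

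**The concern.** The plan speaks of one correlation, but the data support several, and nothing says which of them answers the question. Two things follow. First, each correlation will presumably be judged at 0.05, so the chance of at least one spurious predictor rises with the number run. Second, the site, the between-set reading and the group to highlight can be chosen after the data are seen, and a reader of the results could not tell. A published statement that a given sensory test predicts exercise-induced hypoalgesia would then carry less weight than its p-value suggests.

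**Working it through.** **No figure to reproduce.** The plan states no sample size, no number of correlations and no family-wise error rate. Alpha of 0.05 is taken from the ANOVA paragraph of the Statistical Analysis section, because it is the only level given. Two-sided tests are assumed.

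**Counting the tests** (sites from the Study Protocol section; one response time point and all participants together unless stated):
- One site, or the mean of the two sites, for each measure: 3 predictors × 1 response = 3.
- Sites matched: HPT and PPT each at quadriceps and at trapezius (2 + 2), TS against both responses (2) = 6.
- All sites crossed: (2 HPT + 1 TS + 2 PPT) × 2 responses = 10.
- More than ten: two response time points with all sites crossed give 20. Separate analyses by group would add to any of these counts.

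**Chance of at least one false predictor, independent tests:** 1 − 0.95^k, where k is the number of tests.
- k = 3: 1 − 0.95³ = 0.143
- k = 6: 1 − 0.95⁶ = 0.265
- k = 10: 1 − 0.95¹⁰ = 0.401, with 10 × 0.05 = 0.5 false positives expected

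**Allowing for correlated sites.** This was simulated with no true predictor–response correlation, 10,000 runs per setting, 40, 60 or 90 participants, and the same correlation between sites for HPT, for PPT and for the response. The sample sizes and correlations are assumptions; the documents give neither.

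| Between-site correlation | 10 tests | 6 tests |
|---|---|---|
| 0.5 | 0.36 | 0.25 |
| 0.7 | 0.32–0.33 | 0.24–0.25 |
| 0.9 | 0.25 | 0.21 |

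Sample size made almost no difference.

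**Baseline PPT is a special case.** Suppose hypoalgesia is the later PPT minus baseline PPT, that the two readings have equal variance and correlation r, and that people do not truly differ in response. The covariance of baseline with change is then −(1 − r) times the variance, and the variance of the change is 2(1 − r) times the variance. Their correlation is therefore −√((1 − r)/2):
- r = 0.8: −√0.10 = −0.32
- r = 0.9: −√0.05 = −0.22

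The values of r are assumed. The error rates above take this null correlation as zero, so under a change-score definition they do not cover the baseline PPT test.

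**After correction.** Holm over three tests compares the smallest p-value with 0.05/3 = 0.0167. Over two tests the first step is 0.05/2 = 0.025.

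**The case against.** The strongest reply is that the sentence names three predictors and one outcome, and that collecting data at two sites does not commit the investigators to correlating every site with every other. This stands. A reader might infer from the site lists that at least ten correlations are planned, but ten is only the fully crossed reading, and 6 or 3 fit the wording equally well.

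A reader might also infer a better than one-in-three chance of a false predictor. That needs ten tests and moderate between-site correlation; at 0.9 the ten-test figure is about 25%, and with three tests it is about 14%. A figure of 64% for 20 tests (1 − 0.95²⁰ = 0.642) would treat repeated readings of the same sites in the same people as independent, so it serves only as an upper figure. Nor does the plan break a family-wise rate of its own: "Our a priori alpha level is <0.05" stands in the ANOVA paragraph, and reading each correlation at that level is a reasonable inference, not a quoted rule.

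It can be said, too, that the correlations are exploratory. The plan does not say so, nor does it call them confirmatory; an explicit exploratory label would be an acceptable answer. The claim that Bonferroni already covers them fails, because "Simple effects decomposition with Bonferroni correction were completed" belongs to the ANOVA.

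What survives is that even the most favourable reading leaves three uncorrected tests, and that the plan does not show which reading applies.

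**Conclusion.** The point holds as an unspecified and uncorrected set of tests, not as a fixed count. The plan allows 3, 6, 10 or more correlations. With independent tests and no true predictor, the chance of at least one false finding is 14%, 26% and 40% for the first three counts. Under assumed between-site correlations of 0.5 to 0.9 the ten-test figure is about 36% to 25%. These figures assume that each correlation is read at 0.05. If hypoalgesia is a change from baseline PPT, the baseline PPT test has a further fault that no multiplicity correction removes.

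A reader might infer that the trial's main comparisons are weakened. They are not: the randomised comparisons of PPT and of CPM by group do not depend on these correlations. This is a change that should be made to an association analysis, and it is cheap.

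**What to change.** 1. Name one hypoalgesia response, for example the dominant quadriceps at one stated time point, and say which groups enter the analysis.
2. Use one score per modality: the two-site mean for HPT, the two-site mean for PPT, and TS. Apply Holm across the three tests.
3. Report all site-specific and trapezius correlations with 95% confidence intervals, labelled exploratory.
4. If hypoalgesia is a change from baseline PPT, do not correlate baseline PPT with a change computed from the same reading. Either use one of the two baseline trials as predictor and the other to compute the change, or report that correlation descriptively and apply Holm to HPT and TS only. The split assumes that the errors of the two trials are unrelated, and a single trial is noisier than the mean of two.
5. The document is written largely in the past tense. If the analyses are already done, naming a primary response now would be post hoc. In that case report every correlation that was run and label them all exploratory.

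The cost is wording, with no new data. The downsides are a stricter threshold (0.0167 for the smallest of three p-values) and the loss of confirmatory standing for site-specific results.
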